5.1.2 Treated Population (TP)

The “treated” population is defined as all subjects who have been randomized and treated with any dose of the study drugs.

The safety evaluation will be performed base on treated population (TP).

Safety analyses will be performed based on the treated population. The treated population will also be analyzed for the PK parameters, as supportive evidence to the PK profiles.

5.1.3 Intent-to-treat Population (ITT)

The “Intent-to-Treat” population is defined as all subjects who have been randomized.

5.2 MISSING DATA HANDLING

A table of all missing samples, with explanations, will be provided. Objective criteria for re-assay of samples considered as “pharmacokinetic anomalies” as defined in the Amphastar SOP will be observed. Re-assay analyses and data handling and reporting will be performed according to the approved SOP. Some re-assayed data may be considered as “final” data, where appropriate. Data for all populations and all Study Arms will be analyzed using both original as well as final values.

5.2.1 Missing Data Handling for Evaluable Subjects

For an evaluable subject that was defined in Section 5.1.1, only a small portion of PK measurements, if any, are allowed to be missed, and the interpolation method will be used for imputation.

5.2.2 Missing Data Handling for Non-Evaluable Subjects

Non-Evaluable Subjects will be excluded from PK evaluation.

5.3 STATISTICAL ANALYSIS

5.3.1 Demographic Data

Demographic data including, but not limited to age, race, gender and ethnicity and baseline characteristics such as medical history, vital signs, ECG will be reported for each subject. For all subjects as one group, continuous variables will be summarized with n, mean, standard deviation, while frequency counts and percentage of subjects within each category will be provided for categorical data.

5.3.2 PK Analysis

5.3.2.1 Concentration-time Profile

The concentration-time profile is constructed based on the plasma epinephrine concentration measurements. All concentration-time curves will be plotted for each subject for all treatment arms, and all mean concentration-time curves of all subjects will also be plotted for each treatment arm.

5.3.2.2 PK Parameters

For PK curve, the following main PK parameters will be obtained:

- **Drug Exposure** $AUC_{0-t_m}^{DE}$ for exogenous substance ($t=t_m$ for Treatment-A and B, $t=24\text{hrs}$ for Treatment-C),
- **Drug Exposure** for exogenous substance $AUC_{0-\infty}$ and C_{max} , the peak concentration from the PK curve;
- t_{max} , time corresponding to C_{max} .
- $t_{1/2}$, terminal elimination half-life of each analyte.

PK curves will be fitted with the most suitable PK model by the standard PK analysis software, WinNonlin. The fitted PK parameters will be summarized in tables for all arms. The results will be listed for each subject in each treatment arm. The mean of each treatment arm will also be calculated.

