- Epinephrine concentrations versus time; and
- The mean and standard deviation of study endpoints will be estimated. The variances within and between subjects will be estimated.

4) Statistical Analysis:

All endpoint will be listed and compared between treatments.

VI. Safety Evaluations

- 1) Monitor changes in vital signs and ECG will be analyzed between Screening, designated post-dose time points and EOS;
- 2) Heart rate, and systolic and diastolic blood pressure will be measured at baseline, 5 ± 2 min, 15 ± 5 min, 60 ± 5 min, 120 ± 15 min and 24 ± 2 hours after dosing;
- 3) Monitor serum potassium and glucose at study baseline, designated post-dose time points and EOS;
- 4) Physical examinations at Screening, and at the end of the last Dosing Visit, or study termination;

- 5) The results of laboratory tests, including CBC (with differential), metabolic panel and UA, will be assessed and compared between data at Screening and that at EOS;
- 6) All subjects will be queried for ADEs. All ADEs must be recorded and assessed.

Table of Contents

1. INTRODUCTION AND RATIONALE.....	14
1.1. Introduction of the Drug Product.....	14
1.2. Mechanism of Action	15
1.3. Indications and Dose	15
1.4. Pharmacokinetics (PK) and Pharmacodynamics (PD) Profile	15
1.5. Contraindications, Warnings, Precautions, and Adverse Reactions.....	17
1.5.1. Contraindications	17
1.5.2. Warnings and Precautions.....	17
1.5.3. Adverse Reactions	18
1.6. Drugs with Strong Impact on PK or PD	18
2. OBJECTIVES	20
2.1. Objective.....	20
2.2. Primary Endpoints	20
2.3. Secondary Endpoint.....	20
3. INVESTIGATORS AND STUDY SITES.....	21
3.1. Principal Investigator(s)	21
3.2. Investigational Site(s).....	21
3.3. Laboratory	21
4. MATERIALS AND METHODS	22
4.1. Study Design.....	22
4.2. Study Subjects	22
4.2.1. Sample Size.....	22
4.2.2. Subject Enrollment.....	22
4.2.3. Inclusion Criteria:	22
4.2.4. Exclusion Criteria	23
4.3. Randomization Procedures	23
4.3.1. Subject Identification Assignment.....	23
4.3.2. Subject Randomization	24
4.4. Dispensing, Returning, and Storage of Material and Drug Supplies.....	24
4.5. Study Drugs Administration and Training	25
4.5.1. Training for Correct Use of MDI Inhaler	25
4.5.2. Preparation and Training of MDIs at the Dosing Visit.....	25
4.5.3. Detailed MDI Dosing Procedure	26

4.5.4. IM Injection Procedure	27
4.6. Blinding Methodology and Procedure.....	27
4.7. Unblinding	27
5. STUDY PROCEDURE.....	29
5.1. Global Plan	29

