3. STUDY DESIGN AND OUTCOMES

3.1 STUDY DESIGN

This study is a randomized, safety, evaluator-blinded, single dose, three-treatment, crossover, fasting study in healthy adult volunteers. The treatments and doses evaluated in this study are summarized in Table 1.

Table 1. Treatments and Dose

Items	Treatment-A	Treatment-B	Treatment-C
Study Drug Name	Primatene Mist, E004	Epinephrine Injection Auto-Injector (Generic of EpiPen®)	ProAir
Manufacturer			
API	Epinephrine	Epinephrine	Albuterol Sulfate
Dosage Form	Microcrystalline Suspension HFA MDI	Sterile Solution	Microcrystalline Suspension HFA MDI
Strength	0.125 mg/inh	0.3mg/0.3mL	0.09 mg/inh
Dose Regimen	2 inhalations, 0.25mg	IM Injection of 0.30 mg Epinephrine in 0.30 mL	2 inhalations, 0.180 mg
Route of Administration	Oral Inhalation	IM Injection	Oral Inhalation

The study is conducted in healthy male and female adult subjects at 18 to 50 years of age with a targeted total of 24 evaluable subjects at the completion of study.

The design includes one screening visit, three (3) study visits and a follow-up phone evaluation. All subjects will be screened for enrollment before being randomly assigned to one of the six treatment sequences by 3 x 3 Latin Square method.

According to the randomized treatment sequence, each qualified subject will be treated with one of the three (3) treatments at each study visit. At each study visit, 26 PK blood samples will be collected and plasma will be isolated for analyzing concentrations of albuterol and epinephrine. The three (3) study visits, and main study procedures, are outlined in Summary of Activities below (Table 2):

The three study visits, and main study procedures, are outlined in Study Schema:

Table 2. Summary of Activities in All Visits and EOS

Study Activities & Evaluations	Screen Visit	Dosing Visit-1	Dosing Visit-2 and 3	EOS ¹
Informed Consent / HIPAA	X			
Medical history / demographics	X			
Physical Exam (PE)	X			X
Lab: Urinalysis (UA)	X			X
Lab: CBC/Comp. metab. Panel	X			X
Lab: Thyroid Function	X			
Lab: HIV-Ab, HB-sAg, HCV-Ab	X			
Inclusion/Exclusion	X	X		
Confirmation of enrollment		X		
Assign subject ID		X		
Randomization		X		
Training/Dosing of MDI	X	X	X	
Concomitant Medicines		Record throughout study period		
Urine or serum pregnancy test	X	X	X	
Urine drug screen	X	X	X	
Alcohol screen (urine or breathalyzer)	X	X	X	
Food / beverage restrictions		X	X	
Meals served		X	X	
PK Baseline samples		X (1)	X (1)	
PK samples		X (25)	X (25)	

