4. CALCULATION OF RELATED STATISTICAL QUANTITIES

4.1 PK/PD PARAMETERS

4.1.1 Primary Endpoints

(1) C_{max} , in units of pg/mL, is defined as the maximum of experimental data points of epinephrine or albuterol concentration for a given subject and given treatment:

[figure not shown]
$$C_{max} = \max (C_1 \cdots C_i \cdots C_n) \quad i = 1, 2, 3 \cdots n \quad (1)$$

where C_i is the observed plasma concentration of albuterol or epinephrine at the time t_i ; which is the sampling point time;
 t_1 is the baseline, and n is the number of available PK measurements.

(2) $AUC_{0-t_m}^{Tot}$ for Total API,

As is demonstrated in the left plot of **Figure 1**, the AUC is for total API, including both exogenous and endogenous, if the endogenous active ingredient exists, such as epinephrine for Treatments A and B.

Figure 1 AUC for Total Active Ingredient (left) and Drug Exposure (right)

$AUC_{0-t_m}^{Tot}$ is reported in units of pg/mL*hr, can be calculated per the trapezoidal rule as given the Eq. (2):

$$AUC_{0-t_m}^{Tot} = \sum_{i=1}^{m-1} \frac{C_i + C_{i+1}}{2} (t_{i+1} - t_i) \quad (2)$$

where

- t_m is the time of the first PK point for the subject and the treatment, after C_{max} , that is reduced to the same day baseline (C_0), if C_0 is detectable, such as for epinephrine, (see **Fig. 1**, left plot); and
- $t_m > t_{max}$, and is the smallest time point that meets

$$C(t_m) \leq C_0 + \frac{1}{2} QL \quad (3)$$

- $t_m = 24$ hrs for albuterol, or m is the number of available PK measurements until t_m .

(3) The AUC for Drug Exposure $AUC_{0-t_m}^{DE}$

The AUC for the drug exposure, as is demonstrated in the right plot of **Figure 1**, is the AUC for exogenous API, if the endogenous active ingredient exist such as epinephrine for Treatments A and B.

$AUC_{0-t_m}^{DE}$ is reported in units of pg/mL*hr, and is calculated as follows:

$$AUC_{0-t_m}^{DE} = AUC_{0-t_m}^{Tot} - C_0 t_m \quad (4)$$

where $AUC_{0-t_m}^{Tot}$ and t_m is obtained based on Eqs. (2) and (3).

(4) **Drug Exposure $AUC_{0-\infty}$** (in units of pg/mL*min) is defined as below

$$\begin{cases} AUC_{0-\infty} = AUC_{0-t_m}^{DE} & \text{if } t_m < 24 \text{ hrs} \\ AUC_{0-\infty} = AUC_{0-t_m}^{DE} + AUC_{t_m-\infty}^{DE} & \text{if } t_m = 24 \text{ hrs} \end{cases} \quad (5)$$

$AUC_{t_m-\infty}$ can be obtained per the extrapolation method as given in the Eqs. (6) –(7) below, based on the time is long enough so that

$$C(t) \approx Be^{-k_e t}, \quad (6)$$

thus

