4.1.2 Secondary Endpoints

- (1) t_{max} is an observed value, and is represented in units of “min”,
- (2) $t_{1/2}$, terminal elimination half-life of each analyte will be reported in this study. The half-life of elimination can be calculated using K_e :

$$t_{1/2} = \frac{\ln(2)}{K_e} \quad (10)$$

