5. STATISTICAL DESIGN AND ANALYSIS

5.1 STUDY POPULATION

5.1.1 Per Protocol Population (PPP)

The “Per Protocol” population is defined as all subjects who have received all study medications during the study and are evaluable for all treatments. The primary analyses will be performed based on “Per Protocol” population (PPP).

An evaluable subject for primary analyses of this study must meet all of the following ten (10) items for both treatments:

- (1) Correct dose and administration;
- (2) Nineteen (19) or more of 25 post-dose PK data points (>75%) are available;
- (3) There are no more than four (4) consecutive missing PK data points;
- (4) The baseline PK data point is available;
- (5) For Treatment-A, at least four (4) of the five (5) PK data points at 1, 2, 3, 5, and 7 minutes post-dose are available;
- (6) For Treatment-B, at least four (4) of the five (5) PK data points at 9, 12, 15, 18, and 21 minutes post-dose are available;
- (7) For Treatment-C, at least four (4) of the five (5) PK data points at 25, 30, 40, 50, and 60 minutes post-dose are available;
- (8) For Treatment-A, at least three (3) of the PK data points at 25, 30, 40, and 50 minutes post-dose are available.
- (9) For Treatment-B, at least three (3) of the PK data points at 80, 90, 120 minutes and 4 hours post-dose are available; and
- (10) For Treatment-C, at least three (3) of the PK data points at 6, 8, 12 and 18 hours post-dose are available.

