1	C2-C4 (Min. 1,2,3): 1 ± 0.5	1	0.5 min	0%	0%	0 min	0	-	no flag allowance
2	C5-C7 (Min. 5,7,9): 2 ± 1	2	1 min	0%	0%	0 min	0	-	ibid
3	C8-C11 (Min. 12, 15, 18, 21): 3 ± 1	3	1 min	50%	0%	0 min	0	-	ibid
4	C12-C13 (Min. 25,30): 5 ± 2	5	2 min	25%	25%	0.5 min	0.5	100%	
5	C14-C19 (Min. 40, 50, ...80, 90): 10 ± 5	10	5 min	0%	0%	0 min	0	-	no flag allowance
6	C20-C21 (hr. 2): 120 ± 10	30	10 min	50%	0%	0 min	0		ibid
7	C20-C21 (hr. 4): 120 ± 10	120	10 min	500%	50%	5 min	30	17%	
8	C22-C23 (hr. 6,8): 120 ± 15	120	15 min	300%	300%	45 min	45	100%	
9	C24-C26 (hr. 12, 18,24): 360 ± 20	360	20 min	800%	300%	60 min	40	150%	

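### tmax is to be summarised by arm mean (and SD), with no median or range, although it is read from a grid with gaps of 1 min to 6 h and one late maximum can move the mean by 10 min or more

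*SAP*

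**What the plan says.** SAP 2.2 and Protocol 2.3 make tmax a secondary endpoint. SAP 4.1.2 says it "is an observed value, and is represented in units of" minutes. It is the time of Cmax, which under SAP 4.1.1 "is defined as the maximum of experimental data points of epinephrine or albuterol concentration for a given subject and given treatment". That definition has no baseline correction and no time limit, so the search runs over every available sample to 24 h.

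The sampling grid is very uneven. SAP Table 4 runs from "C2-C4 (Min. 1,2,3): 1 ± 0.5" (minutes) to "C24-C26 (hr. 12, 18,24): 360 ± 20" (minutes), that is, from gaps of 1 min to gaps of 6 h.

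On summaries, SAP 5.3.2.2 lists tmax among the main PK parameters, plans a listing by subject, and then states: "The mean of each treatment arm will also be calculated". The SD appears only in the Protocol, synopsis V.3: "The mean and standard deviation of study endpoints will be estimated". Synopsis V.4 adds that endpoints will be compared between treatments. Neither document names a median, a range or a rank-based summary for tmax.

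**The concern.** A variable read from an uneven grid with a long upper tail is poorly described by a mean. Most Primatene values should lie within a few minutes of dosing, but the grid allows values up to 1,440 min, and a single one of those can dominate a mean of 24 numbers. The SD then mainly reflects that one subject.

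A late maximum is conceivable for inhaled epinephrine. The expected rise may be modest against endogenous epinephrine, while Protocol 5.3.3 lifts movement restrictions after the 120-minute sample and allows meals after the 4-hour sample. An endogenous rise later in the day could therefore be recorded as Cmax and set tmax.

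At stake is the reported contrast in time to peak between inhaled and injected epinephrine. Means could show Primatene peaking as late as the injection, or later, because of one or two subjects.

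**Working it through.** The documents state no tmax figure, so there is nothing to reproduce.

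**Inputs**
- Subjects: n = 24. SAP 3.1 describes a study "with a targeted total of 24 evaluable subjects at the completion of study".
- Post-dose times (SAP Table 3): 1, 2, 3, 5, 7, 9, 12, 15, 18, 21, 25, 30, 40, 50, 60, 70, 80, 90, 120 min and 4, 6, 8, 12, 18, 24 h. Smallest gap 1 min, largest 360 min.
- Likely peak windows (assumption, from SAP 5.1.1). For Treatment A, "at least four (4) of the five (5) PK data points at 1, 2, 3, 5, and 7 minutes post-dose are available"; the matching rule for Treatment B covers 9 to 21 min. These are data-completeness rules, read here as a hint of where peaks are expected.

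**Effect of one late value.** Moving one of n values from a to T shifts the mean by (T − a)/n. With a = 3 min and n = 24:
- T = 4 h: (240 − 3)/24 = 9.9 min
- T = 6 h: (360 − 3)/24 = 14.9 min
- T = 24 h: (1440 − 3)/24 = 59.9 min

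**When this exceeds the A-B difference d.** The condition is T > a + n·d.

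| Reading of the windows | d (min) | Threshold (min) | First sample that exceeds it |
|---|---|---|---|
| Nearest edges, 7 and 9 | 2 | 7 + 24×2 = 55 | 60 min |
| Midpoints, 4 and 15 | 11 | 4 + 24×11 = 268 | 6 h |
| Middle sampling times, 3 and 15 | 12 | 3 + 24×12 = 291 | 6 h |
| Outer edges, 1 and 21 | 20 | 1 + 24×20 = 481 | 12 h |

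**Median against mean and SD.** Take an illustrative Primatene arm with the values 1, 2, 3, 3, 5, 7 min, four times each. The mean is 3.5, the SD 2.0 and the median 3 min. If one 3-min value becomes 6 h, the mean is 18.4 and the SD 72.8. If it becomes 24 h, they are 63.4 and 293.2. The median stays at 3 in both cases.

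**Size of the Primatene rise.** Protocol 1.4 reports a baseline of 0.23 nmol/L, and peaks of 1.50 after 2.4 mg and 4.22 after a further 4.8 mg. Its own conversion is 275/1.50 = 183 pg/mL per nmol/L, so the baseline is about 42 pg/mL. Scaling the rise in proportion to 0.25 mg (assumption):
- (1.50 − 0.23) × 0.25/2.4 = 0.132 nmol/L, about 24 pg/mL
- (4.22 − 0.23) × 0.25/4.8 = 0.208 nmol/L, about 38 pg/mL

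The within-subject CV is not given. The reported ±0.02 on 0.23 (n = 6) is 9% if it is an SD and 0.02 × √6/0.23 = 21% if it is a standard error; both are between-subject figures. The range used below is 9% to 25%.

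**Simulation.** 1,600 trials of 24 subjects on the plan's schedule; true peak 2 min, endogenous level 42 pg/mL, independent lognormal noise, decay half-life 3 to 5 min (all assumed). The spread within a cell reflects the assumed curve shape.

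| Rise (pg/mL), CV | Mean, search to 120 min | Mean, search to 24 h | Median, either search |
|---|---|---|---|
| 24, 25% | 9.5 to 11.7 | 46 to 65 | 2.9 to 3.6 |
| 24, 15% | 3.7 to 3.9 | 8 to 11 | 2.2 to 2.6 |
| 24, 9% | 2.3 to 2.7 | 2.4 to 2.7 | 2.0 to 2.2 |
| 38, 25% | 4.9 to 5.0 | 15 to 19 | 2.4 to 2.8 |
| 38, 9 to 15% | 2.2 to 2.9 | 2.2 to 3.0 | 2.0 to 2.3 |
| 80, 9 to 25% | 2.1 to 3.0 | 2.1 to 3.1 | 2.0 to 2.4 |

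In every setting the median was at least as close to the assumed 2 min as the mean.

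**The case against.** The strongest case against the point is that little depends on it. tmax is secondary and descriptive, with no test planned. Values are listed by subject and all individual curves are plotted, so an outlying tmax would be seen. The SAP says the mean will also be calculated, which does not exclude a median, and the output template is an attachment not included in the documents. All of this stands and limits the consequence. It does not make the mean a suitable summary, nor does it name a better one in advance.

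A reader might also infer more than the documents support:
- **That any late value outweighs the whole A-B difference.** No expected tmax or difference is stated; 11 to 12 min is inferred from completeness rules. At that size a 4 h value (9.9 min) is not enough.
- **That the distortion is large in general, even with the search limited to the early hours.** A mean near 12 min arises only with the smallest rise and the highest CV. With a rise of 38 pg/mL the mean over 120 min is about 2 to 5 min.
- **That both documents prescribe the SD.** The SAP sentence gives only the mean.
- **That tmax can take only scheduled values.** The SAP does not say whether nominal or actual times are used. The grid is uneven either way.
- **That a median cures the late maxima.** It only makes the summary insensitive to them.

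**Conclusion.** The point holds as a minor improvement to a secondary summary. The documents name only mean and SD for a variable on a grid with gaps from 1 min to 6 h, and set no time limit on the maximum. The shift from one late value (9.9 min at 4 h, 14.9 min at 6 h, 59.9 min at 24 h) is plain arithmetic, given 24 subjects and a usual value of 3 min. That one value at 6 h or later exceeds the A-B difference is conditional on a difference of about 11 to 12 min; over the possible 2 to 20 min, the value needed runs from 60 min to 12 h.

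The simulated range for the arm mean (about 2 to 12 min over 120 min, about 2 to 65 min over 24 h) depends on the assumed rise, CV and curve shape, and at a rise of 80 pg/mL mean and median nearly agree. The large 24-hour figures reflect the uncorrected, unlimited Cmax search at least as much as the choice of summary. No primary conclusion is affected.

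**What to change.** In SAP 5.3.2.2 and Protocol synopsis V.3, state that tmax is summarised by median, minimum and maximum per treatment, and that A versus B is described by the median within-subject difference. A Hodges-Lehmann confidence interval for that difference is optional, since the plan specifies no interval for any other endpoint. State also whether nominal or actual sampling times are used.

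The cost is a sentence or two in each document and a changed table template. Samples, visits and sample size stay as they are. Making the change before concentrations are seen avoids a post hoc choice of summary. How far in time Cmax is searched, and whether it is baseline-corrected, is a separate matter for SAP 4.1.1.

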5.3.2.3 Relative Bioavailability (RBA)

The relative bioavailability of Treatment-A (E004 Inhalation) over Treatment-B (IM) can be defined as follows:

$$RBA = \frac{AUC_{0-\infty}^A}{AUC_{0-\infty}^B} \quad (11)$$

RBA data for each subject of are to be calculated and tabulated. The mean RBA of Treatment-A over Treatment-B of all subjects will be calculated and summarized for comparison.

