6.2.4 Relative Bioavailability

The relative bioavailability of Treatment-A over Treatment-B (IM) can be defined as follows:

$$RBA = \frac{AUC_{0-\infty}^A}{AUC_{0-\infty}^B}$$

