Attachment:

Template of Statistical Analysis Output for Clinical Study Protocol No. API-E004-CL-I
(Available Upon Request)

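### The SAP summarises the inhaled-versus-IM epinephrine comparison by a mean of individual AUC ratios with no interval or log-scale analysis, and labels an undivided ratio relative bioavailability

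*SAP*

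**What the plan says.** SAP section 1 presents the trial as a head-to-head crossover comparison of systemic exposure among the three treatments. The protocol synopsis (section V, Study Evaluations) says "All endpoint will be listed and compared between treatments". It adds "The mean and standard deviation of study endpoints will be estimated" and "The variances within and between subjects will be estimated".

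The SAP turns this into the following:

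- **SAP 5.3.2.2:** fitted parameters in tables for all arms, results listed by subject, and "The mean of each treatment arm will also be calculated". No SD, CV or geometric mean is named for PK parameters, although SAP 5.3.3 names n, mean and SD for the safety variables.
- **SAP 5.3.2.3, Eq. (11):** "The relative bioavailability of Treatment-A (E004 Inhalation) over Treatment-B (IM) can be defined as follows", followed by AUC0-∞ under A divided by AUC0-∞ under B. The ratio is computed and tabulated for each subject, and then: "The mean RBA of Treatment-A over Treatment-B of all subjects will be calculated and summarized for comparison".
- **Protocol 6.2.4:** the same undivided ratio, introduced by "The relative bioavailability of Treatment-A over Treatment-B (IM) can be defined as follows".

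SAP Table 1 gives the doses as 0.25 mg for A and 0.30 mg for B. The SAP also names an attachment, "Template of Statistical Analysis Output for Clinical Study Protocol No. API-E004-CL-I", which is available on request and was not seen.

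**The concern.** A within-subject comparison is the purpose of this crossover, yet its planned summary is one average with no statement of uncertainty. Three things are at stake.

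1. **Averaging.** Ratios are skewed, and their arithmetic mean sits above their geometric mean. The headline figure therefore depends on which mean is used, and the SAP does not qualify the word.
2. **Precision.** With about 24 evaluable subjects the ratio may be known only loosely. Arm means and a mean ratio do not show this. The SDs and variance components promised in the protocol synopsis are not carried into the SAP's PK section, and no interval level is fixed before the data are seen.
3. **Label.** A reader who takes relative bioavailability at its name will read a dose-for-dose figure. What is reported is exposure at two different administered doses.

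**Working it through.** The plan gives no figure of its own to reproduce: no CV, alpha, power or margin is stated. The dose factor below is exact at nominal doses. The rest is illustrative.

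**Inputs from the documents.** Doses 0.25 and 0.30 mg (SAP Table 1); 24 evaluable subjects (protocol 4.2.1); Eqs. (1) to (5) and (11) of the SAP.

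**Assumed.** Log-normal AUCs, the same within-subject CV under A and B, no subject-by-treatment variance, and CVs of 30, 40, 50 and 60%.

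**Dose term.** Dose-normalised ratio = (AUC_A/0.25)/(AUC_B/0.30) = (0.30/0.25) × AUC_A/AUC_B = 1.20 × the Eq. (11) value. Conversely, Eq. (11) gives 0.25/0.30 = 0.833 of it.

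**Averaging.** Let s² = ln(1 + CV²). The log of an individual A/B ratio has variance 2s², so expected mean ratio / geometric mean ratio (GMR) = exp(s²) = 1 + CV². This factor does not depend on the true ratio. A simulation of 200,000 trials with n = 24 gave the median of sample mean ratio over sample GMR shown in the table.

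**Precision.** The 95% interval is GMR multiplied or divided by exp(t × s × √(2/24)). A crossover model on A and B only has 48 observations less 24 for subjects (including the mean), 1 for treatment and 2 for period, leaving 21 df (t = 2.080). A paired log analysis has 23 df (t = 2.069).

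| Assumed CV | s² | Expected mean / GMR | Simulated median, n = 24 | 95% factor, df 21 | 95% factor, df 23 |
|---|---|---|---|---|---|
| 30% | 0.0862 | 1.09 | 1.083 | 1.193 | 1.192 |
| 40% | 0.1484 | 1.16 | 1.146 | 1.260 | 1.259 |
| 50% | 0.2231 | 1.25 | 1.226 | 1.328 | 1.326 |
| 60% | 0.3075 | 1.36 | 1.322 | 1.395 | 1.393 |

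Example at 50%: s = √0.2231 = 0.4724; 2.080 × 0.4724 × 0.2887 = 0.2836; exp(0.2836) = 1.328. The two methods agree to within 0.002, so the choice between them matters little. The level matters more: at 90% the df 21 factors run from 1.157 to 1.317.

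**Zero or negative AUC.** Eq. (1) includes the baseline among the values from which Cmax is taken. Suppose the baseline C0 is the maximum. The first post-dose value C, at time t, then already satisfies Eq. (3), so tm = t. Taking C0 as the value at time 0, Eqs. (2) and (4) give (C0 + C)/2 × t − C0 × t = (C − C0) × t/2, which is zero or negative. Eq. (5) passes this to AUC0-∞ because tm is below 24 hours, and Eq. (11) then uses it. No rule covers such a value in a ratio or a logarithm.

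**The case against.** The strongest reply is that this is a descriptive exposure study. Its objective is to assess an exposure profile. It states no hypothesis, margin or decision rule, and the protocol synopsis lists relative bioavailability as an additional evaluation. On that view a tabulated ratio per subject and its mean are enough, and a reader could work out an interval from the listing. This stands as far as it goes: nothing planned becomes invalid. It does not explain why the level and scale of the main comparison are left open in the visible text.

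Other parts of the reply also stand:

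- A reader might infer that the plan has no estimator or ignores the pairing. It does neither. SAP 5.3.2.3 fixes a within-subject ratio in the direction A over B, and SAP 5.1.1 restricts the primary analysis to subjects evaluable for all treatments.
- Arithmetic is an inference. The SAP writes only mean, and the 9 to 36% rests on the ordinary reading of that word and on assumed CVs.
- The undivided ratio is a legitimate measure of exposure at the administered doses and answers the stated objective. Only the name misleads, and the factor 1.20 is recoverable from the printed doses.
- A reader might infer that zero or negative AUC will be common under Treatment A. The equations allow it, but the documents do not show how often it would occur. The log-normal illustration assumes positive AUCs and cannot settle that.
- Protocol 4.7 mentions BE analyses in passing. No BE limits are set, so the plan cannot be read as a bioequivalence test lacking its interval.

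**Conclusion.** The point holds in a limited form. The visible SAP text summarises the central A-versus-B comparison by arm means and an unqualified mean of individual AUC0-∞ ratios, with no interval, level or log-scale analysis. It also does not carry forward the PK SDs and variance components that the protocol promises.

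- **Certain at nominal doses:** the quantity called relative bioavailability is 0.833 of the dose-normalised value.
- **Illustrative:** at assumed CVs of 30 to 60%, an arithmetic mean of ratios is expected to exceed the GMR by 9 to 36%, and a 95% interval with 24 subjects spans the GMR multiplied or divided by about 1.19 to 1.40.

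The averaging effect pushes the reported figure up and the missing dose term pushes it down, so they should not be quoted as one net bias. A reader might go further and conclude that the study cannot support its comparison or that a planned conclusion is wrong. The documents do not support that: the ratios are tabulated, the study is descriptive and no decision depends on this ratio. The finding is confined to the text available, because the output template may hold more.

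**What to change.** 1. **Method and interval (SAP 5.3.2).** Analyse ln(AUC0-∞) and ln(Cmax) of epinephrine for Treatments A and B. Both analytes are assayed at every visit, but only A and B deliver epinephrine. Name one method: a crossover model with sequence, period and treatment fixed and subject random, or a paired log-scale analysis. Report the A/B geometric mean ratio with a confidence interval at a pre-stated level, beside the individual ratios. If the output template already contains a method and interval, move that text into SAP 5.3.2.
2. **Dose term or name (protocol 6.2.4 and SAP Eq. (11)).** Either define RBA = (AUC0-∞(A)/0.25)/(AUC0-∞(B)/0.30), which is 1.20 times the present ratio, or rename the present ratio as the exposure ratio at the administered doses. No change of dose is implied.
3. **Zero or negative AUC.** Report the number per treatment. State in advance that, if any occur, the main A/B AUC summary is the ratio of arithmetic means over all evaluable subjects with a Fieller interval. That needs no logarithms and drops no one. Show the log analysis without those subjects only as supportive, and note that it leaves out the lowest exposures.

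The cost is a short SAP subsection, one formula or name changed in two documents, and slightly more analysis. No new data are needed.
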